Shift tables for hematology and biochemistry parameters will be constructed, based upon normal ranges and GW toxicity limits (See Section 8), to determine the categorical shifts from baseline to each post-baseline visit. Values will be categorized as 'Normal', 'Low' or 'High' based on normal ranges and 'Toxicologically Low', 'Toxicologically Normal' or 'Toxicologically High' based on GW toxicity limits.

For eGFR, results will be assigned to the following grades:

- Normal: $>60 \text{ ml/min}/1.73 \text{ m}^2$
- Grade 1: $60 \text{ ml/min}/1.73 \text{ m}^2$
- Grade 2: $\geq 30 \text{ and } < 60 \text{ ml/min}/1.73 \text{ m}^2$
- Grade 3: $\geq 15 \text{ and } < 30 \text{ ml/min}/1.73 \text{ m}^2$
- Grade 4: $< 15 \text{ ml/min}/1.73 \text{ m}^2$

A separate shift table will be produced for eGFR based upon the above grades to determine the categorical shifts from baseline to each post-baseline visit.

For the blinded phase, scatter plots will be produced for each laboratory parameter presenting the maximum post baseline result divided by the upper limit of normal (ULN) on the Y-axis, and the baseline result divided by the ULN on the X-axis. However, for prothrombin international normalized ratio (INR), both axes will present the raw results rather than dividing by ULN.

An additional table will be produced for the blinded phase only, summarizing the number of patients meeting the following criteria:

- Alanine aminotransferase (ALT) $> 1 \times \text{ULN}$ at baseline
- Aspartate aminotransferase (AST) $> 1 \times \text{ULN}$ at baseline
- AT $> 1 \times \text{ULN}$ at baseline
- Treatment emergent ALT $> 3 \times \text{ULN}$, $> 5 \times \text{ULN}$ and $> 8 \times \text{ULN}$
- Treatment emergent AST $> 3 \times \text{ULN}$, $> 5 \times \text{ULN}$ and $> 8 \times \text{ULN}$
- Treatment emergent AT $> 3 \times \text{ULN}$, $> 5 \times \text{ULN}$ and $> 8 \times \text{ULN}$
- Treatment emergent AT $> 3 \times \text{ULN}$ and either bilirubin $> 2 \times \text{ULN}$ or INR > 1.5

where AT is AST or ALT, and treatment emergent is defined as criteria not met at baseline but met at any time post-baseline. The above will be summarized overall and for the following subgroups:

- Sex (Male, Female).

- Valproic acid use (Yes, No).
- Clobazam use (Yes, No).
- Valproic acid use and Clobazam use (Yes/Yes, Yes/No, No/Yes, No/No).
- Patients taking 3 or more current AEDs.
- Patients taking 4 or more current AEDs.

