Appendix 4 Toxicity Criteria for Laboratory Parameters

The toxicity criteria that will be used to identify abnormal laboratory parameters are presented in Table 12 and

Table 13.

Table 12 Toxicity Criteria for Biochemistry Parameters

Parameter	Toxicity Decrease	Toxicity Increase
Chloride	$\leq 0.96 \times \text{LL}$	$\geq 1.04 \times \text{UL}$
Calcium	$\leq 0.89 \times \text{LL}$	$\geq 1.16 \times \text{UL}$
Sodium	$\leq 0.96 \times \text{LL}$	$\geq 1.04 \times \text{UL}$
Potassium	$\leq 0.90 \times \text{LL}$	$\geq 1.10 \times \text{UL}$
Glucose (mmol/L)	≤ 3.2	≥ 16
Phosphate	$\leq 0.79 \times \text{LL}$	
Cholesterol	$\leq 0.85 \times \text{LL}$	$\geq 1.6 \times \text{UL}$
AST		$\geq 3 \times \text{UL}$
ALT		$\geq 3 \times \text{UL}$
Lactate Dehydrogenase		$\geq 2.6 \times \text{UL}$
Alkaline phosphatase		$\geq 2 \times \text{UL}$
Gamma GT		$\geq 2.6 \times \text{UL}$
Bilirubin		$> 2 \times \text{UL}$
Albumin	$\leq 0.84 \times \text{LL}$	
Total protein	$\leq 0.84 \times \text{LL}$	$\geq 1.16 \times \text{UL}$
Urea		$\geq 2.6 \times \text{UL}$
Blood urea nitrogen		$\geq 2.6 \times \text{UL}$
Creatininine		$\geq 2.6 \times \text{UL}$
Uric acid		$\geq 1.16 \times \text{UL}$

UL = upper limit of reference range

LL = lower limit of reference range

Table 13 Toxicity Criteria for Hematology Parameters

Parameter	Toxicity Decrease	Toxicity Increase
Hemoglobin (g/dL)	≤9.4	
Hematocrit (%)	≤28	
Red cell count	≤0.84xLL	
Mean corpuscular volume	≤0.84xLL	≥1.11xUL
Mean corpuscular hemoglobin	≤0.84xLL	
Mean corpuscular hemoglobin concentration	≤0.84xLL	
Platelets ($\times 10^9$ /L)	≤74	
Prothrombin time		>1.5xUL
Prothrombin international normalized ratio		>1.5
Total white blood cell count ($\times 10^9$ /L)	≤2.9	≥21
Total neutrophil count ($\times 10^9$ /L)	≤1.36	≥14.7
Segmented neutrophil count ($\times 10^9$ /L)	≤0.75	≥12.3
Eosinophils ($\times 10^9$ /L)		≥1.5
Basophils ($\times 10^9$ /L)		≥0.31
Monocytes ($\times 10^9$ /L)		≥2.1
Lymphocytes ($\times 10^9$ /L) for patients <18 years (auto hematology)	≤1.0	
Lymphocytes ($\times 10^9$ /L) for patients <18 years (manual hematology)	≤0.2	
Lymphocytes ($\times 10^9$ /L) for patients ≥18 years	≤0.2	

UL = upper limit of reference range

LL = lower limit of reference range

Appendix 5 Derivation Instructions for Achenbach Child Behavior Checklists and Adult Behavior Checklist

CBCL/1½–5

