Figure 9.12	Cumulative Distribution Function for Absence Seizures During the Treatment Period	ITT Analysis Set
Figure 9.13	Cumulative Distribution Function for Myoclonic Seizures During the Treatment Period	ITT Analysis Set

Figure 9.14	Cumulative Distribution Function for Partial Sensory Seizures During the Treatment Period	ITT Analysis Set
Figure 9.15	Cumulative Distribution Function for Infantile or Epileptic Spasms During the Treatment Period	ITT Analysis Set
Figure 9.16.1	Kaplan-Meier Plot of Time to Baseline TSC-associated Seizure Frequency from the Start of the Treatment Period (Day 1)	ITT Analysis Set
Figure 9.16.2	Kaplan-Meier Plot of Time to Baseline TSC-associated Seizure Frequency from the Start of the Maintenance Period (Day 29)	ITT Analysis Set
Figure 14.1.1	Box Plot of Change from Baseline to the End of Treatment Visit in IGF-1 Levels by Tanner Stages at Baseline	Safety Analysis Set
Figure 14.1.2	Scatter Plot of Change from Baseline to the End of Treatment Visit in IGF-1 Levels Against Weight at Baseline	Safety Analysis Set
Figure 14.1.3	Scatter Plot of Change from Baseline to the End of Treatment Visit in IGF-1 Levels Against Height at Baseline	Safety Analysis Set
Figure 14.1.4.1.X	Scatter Plot of Shift from Baseline to Maximum Post First Dose Laboratory Result - Hematology	Safety Analysis Set
Figure 14.1.4.2.X	Scatter Plot of Shift from Baseline to Maximum Post First Dose Laboratory Result - Biochemistry	Safety Analysis Set
Figure 14.2.1.1.1	Dot Plot of Individual CBD Plasma Concentration vs. Time Profiles, Visit 3, 25 and 50 mg/kg/day (Linear Scale)	Safety Analysis Set
Figure 14.2.1.1.2	Dot Plot of Individual CBD Plasma Concentration vs. Time Profiles, Visit 3, 25 and 50 mg/kg/day (Semi-Log Scale)	Safety Analysis Set
Figure 14.2.1.2.1	Dot Plot of Individual 7-OH-CBD Plasma Concentration vs. Time Profiles, Visit 3, 25 and 50 mg/kg/day (Linear Scale)	Safety Analysis Set
Figure 14.2.1.2.2	Dot Plot of Individual 7-OH-CBD Plasma Concentration vs. Time Profiles, Visit 3, 25 and 50 mg/kg/day (Semi-Log Scale)	Safety Analysis Set
Figure 14.2.1.3.1	Dot Plot of Individual 7-COOH-CBD Plasma Concentration vs. Time Profiles, Visit 3, 25 and 50 mg/kg/day (Linear Scale)	Safety Analysis Set
Figure 14.2.1.3.2	Dot Plot of Individual 7-COOH-CBD Plasma Concentration vs. Time Profiles, Visit 3, 25 and 50 mg/kg/day (Semi-Log Scale)	Safety Analysis Set

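### The laboratory scatter plots use the maximum over the ULN for every parameter, which is the wrong direction where the SAP's toxicity limit is a decrease and only half the picture where it is two-sided

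*SAP*

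**What the plan says.** SAP 5.6.3.1 states that "scatter plots will be produced for each laboratory parameter" in the blinded phase. It describes the vertical axis as "presenting the maximum post baseline result divided by the upper limit of normal (ULN) on the Y-axis"; baseline, scaled to the same limit, goes on the horizontal axis. The one exception is INR, for which "both axes will present the raw results rather than dividing by ULN"; it is still a maximum.

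SAP Appendix 6, Table 21, carries the same rule into the figure titles: "Scatter Plot of Shift from Baseline to Maximum Post First Dose Laboratory Result - Hematology" (Figure 14.1.4.1.X) and "Scatter Plot of Shift from Baseline to Maximum Post First Dose Laboratory Result - Biochemistry" (Figure 14.1.4.2.X). The table lists no version based on the minimum or the lower limit of normal.

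SAP Appendix 4 gives the direction in which each parameter counts as toxic, in Table 12 for biochemistry and in "Table 13 Toxicity Criteria for Hematology Parameters". Many of those limits are decreases. The eGFR grades in SAP 5.6.3.1 also worsen downwards.

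**The concern.** A plot of each patient's most extreme on-treatment value against baseline is useful only if the extreme is taken in the adverse direction. For a parameter whose limit is a fall, the maximum over visits is the patient's best value, and the ULN is not the limit of interest. For a two-sided parameter the plot covers rises only.

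At stake is how readily the figures show falls in blood counts, albumin or electrolytes. A patient with a toxic nadir at one visit and near-normal values at the others would look unchanged.

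**Working it through.** The plan states no figure for this point, so there is nothing to reproduce. The check has three parts.

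**1. Which parameters are affected (SAP Appendix 4)**

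| | Rows | Decrease only | Both directions | Increase only |
|---|---|---|---|---|
| Hematology (Table 13) | 18 | 9 | 4 | 5 |
| Biochemistry (Table 12) | 19 | 2 | 7 | 10 |
| Total | 37 | 11 | 11 | 15 |

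So 11 + 11 = 22 of 37 rows have a decrease limit. Lymphocytes take three rows; counted once, hematology has 16 parameters, of which 7 are decrease only and 4 two-sided, giving 11 of 16.

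Not every row is measured. The laboratory panel in protocol 9.2.9 (Table 9.2.9-1) does not list MCHC, phosphate or chloride. Without MCHC the hematology count is 6 + 4 = 10 of 15. Hemoglobin, hematocrit, red cells, platelets, white cells with differential, albumin, sodium and potassium are all on the panel.

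**2. What the maximum does to a fall**

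Inputs: the protocol schedule (Appendix 1) takes post-dose blood at Visits 4, 5, 6, 7, 9 and 10, so k = 6, or k = 7 for patients who taper and attend Visit 11. Assumption, not in the documents: baseline and post-dose values vary independently and normally within a patient with equal SD.

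- *No change.* The chance that the maximum exceeds baseline is k/(k+1): 6/7 = 86% or 7/8 = 88%.
- *Large late fall, k = 6.* Only the m unaffected visits matter, so the chance is about m/(m+1). A fall at the last visit only (m = 5) gives 5/6 = 83%; at the last three visits (m = 3), 3/4 = 75%.
- *Fall of d SDs at every visit.* The chance is 1 − ∫ φ(b) Φ(b+d)^k db, where φ and Φ are the standard normal density and distribution function. For the minimum, the chance of lying below baseline is 1 − ∫ φ(b) [1 − Φ(b+d)]^k db.

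| Sustained fall d (SDs) | Maximum above baseline, k = 6 / 7 | Minimum below baseline, k = 6 / 7 |
|---|---|---|
| 0 | 86% / 88% | 86% / 88% |
| 1 | 59% / 61% | 97% / 98% |
| 2 | 27% / 29% | >99% / >99% |
| 3 | 7% / 8% | >99% / >99% |

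A fall at one visit barely moves the plotted point (86% to 83%). A large fall at every visit does move it. The first row shows that the minimum has the same drift in the opposite direction when nothing has changed, so which side of the identity line a point lies on says little under either rule.

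**3. An invented platelet series (×10⁹/L)**

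Baseline 250; post-dose 240, 70, 180, 235, 238, 245, 242; assumed ULN 400 to 450. The nadir of 70 meets the Table 13 limit of 74 or less. The planned plot shows 245/400 = 0.61 (or 245/450 = 0.54) against a baseline of 250/400 = 0.63 (or 250/450 = 0.56), which looks like no change. On the same scale the nadir would be 70/400 = 0.18 (or 70/450 = 0.16).

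**The case against.** The strongest reply is that falls are reported elsewhere. SAP 5.6.3.1 plans summaries and change from baseline at every visit, shift tables with low and toxicologically low categories at every post-baseline visit, a table of results indicative of an adverse event, and listings of all laboratory data and of abnormal values. Under SAP 5.1 the summaries include the minimum. That stands: a reader might infer that falls go unreported or that these plots are the only output showing them, and the documents do not support either. What remains is narrower. Those tables work visit by visit, and the listings hold the raw values; no table or figure brings together each patient's worst decrease across treatment. The SAP does take an any-time approach for liver enzyme rises (5.6.3.1) and for flagged vital signs, low values included (5.6.4.1).

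A reader might also infer that the figures cannot show a cytopenia. Part 2 of the working contradicts this: a large fall present at every visit lowers the maximum too, so it appears in weakened form. Nor does the SAP say that the plots are split by arm, so a lost comparison between arms cannot be claimed.

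For eGFR the reply largely succeeds. It is derived from creatinine, whose limit is an increase, so maximum creatinine over the ULN already points the adverse way, and eGFR has its own graded shift table.

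Finally, the figures are descriptive, with no test or decision rule attached. That limits the weight of the point but does not make the maximum the right value to plot.

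**Conclusion.** The point holds as a defect of these figures, not of the laboratory reporting as a whole. Followed exactly, SAP 5.6.3.1 plots the least worrying value against the wrong reference limit for decrease-only parameters, and one direction only for two-sided ones. In hematology this touches 11 of 16 Appendix 4 parameters, or 10 of 15 once MCHC is set aside. The rule is right for parameters with an increase limit only, such as ALT, AST and bilirubin.

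Transient and partial falls are hidden; sustained falls are weakened in proportion to their size. The direction follows from the documents alone. The percentages rest on the independence and equal-variance assumption and are illustrative, as is the platelet series. No efficacy result or error rate is affected. This is a cheap improvement to the safety display.

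**What to change.** In SAP 5.6.3.1 and Table 21:

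- Keep maximum over ULN for parameters with an increase limit in Appendix 4, with INR raw as now.
- For each measured parameter with a decrease limit, add a plot of the minimum post-first-dose result against baseline. Scale both axes to the LLN where the limit is a multiple of the lower limit (for example red cells, MCV, MCH, albumin, sodium, potassium).
- Use raw values where the limit is absolute: hemoglobin, hematocrit, platelets, white cells, both neutrophil counts and lymphocytes (7 of the 11 hematology parameters), and glucose. An absolute limit becomes a single line on an LLN-scaled axis only if all patients share one LLN, which is doubtful for ages 1 to 65. The lymphocyte limits also differ by age and, under 18, by counting method, so they need separate panels or lines.
- Produce both plots for two-sided parameters.
- Draw the Appendix 4 limit on each plot as the reference, since the identity line does not discriminate under either rule.
- Optionally, add the raw minimum for eGFR.

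The cost is SAP wording, a changed summary function in one figure program and some extra figures. No new data are needed.
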